## **Evaluation of the Wisdom Enhancement Timeline Approach for Post-Stroke Depression Using a Single-Case Experimental Design**

[name]1a, [name], [name]

**Date:** 26/03/2024

This study will aim to answer the question: *Does enhancing wisdom through the timeline technique improve mood in post-stroke depressed individuals?* Additionally, it will examine whether enhancing wisdom restores identity continuity and improves self-esteem.

It is hypothesised that wisdom will improve first, followed by gains in identity clarity or self-esteem, as structured self-reflection fosters agency and self-worth. Finally, mood regulation is expected to improve last, aligning with findings that emotional stabilisation follows meaning-making and self-affirmation rather than occurring simultaneously (Beaumont, 2009).

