### **Methods**

#### **Design**

A single-case experimental multiple-baseline design (MBD) will be adopted. Following Christ's (2007) recommendations, the study will pre-specify hypotheses, predetermine baseline durations, and randomise allocation via Random.org. Participants will be assigned to baseline durations of 2, 3, or 4 weeks, with non-concurrent intervention introduction to enhance flexibility. The independent variable will be the intervention, and the dependent variables will be mood, wisdom, identity, and self-esteem, measured repeatedly. Blinding will not be implemented due to feasibility constraints.

Although stability is generally recommended before intervention, Krasny-Pacini and Evans (2018) suggest that five baseline data points are sufficient to distinguish natural fluctuations from intervention effects. Replication will be built into the multiple-baseline design, with each participant serving as an independent test of the intervention's effects. Initially, a one-month follow-up review will be planned; however, this may be omitted if time does not permit.

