#### **Idiographic Visual Analogue Scale**

The primary outcome will be assessed using a Visual Analogue Scale (VAS), a widely used measure

for tracking subjective experiences in clinical research (McCormack et al., 1988). Participants will rate their agreement with four daily statements on vertically presented 10 cm scales, with higher scores indicating stronger agreement. VAS items will be aligned with the research questions and reviewed for relevance by individuals with lived stroke experience via the university's Personal and Public Involvement (PPI) database.

The four VAS items will be:

1. Today, my mood is good (VAS\_mood)
2. Today, I feel able to accept the person I am/Today, I feel like I am adapting to life after my stroke (identity; VAS\_ID)
3. Today, I feel good about myself (self-esteem; VAS\_SE)
4. Today, I feel that I can use the wisdom of my life to help me deal with my current problems (VAS\_wisdom)

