### **Analysis**

Both single-case visual and statistical techniques will be used following best practices (Harrington & Velicer, 2015; Manolov & Moeyaert, 2017). Visual analysis will assess phase variability using a  $\pm 25\%$  stability envelope (Lane & Gast, 2014). Higher percentages will indicate greater stability, and lower percentages will reflect greater variability.

To assess whether VAS ratings during the intervention phase are higher than baseline, Tau-U (Parker et al., 2011) will be implemented. It will account for baseline trends, effect sizes, and phase non-overlap. Resistant to autocorrelation, Tau-U provides strong statistical power in small datasets (Parker et al., 2014). Interpretations will follow Vannest and Ninci's (2015) guidelines, with baseline corrections applied as needed to prevent inflated effect sizes.

Piecewise regression (Center et al., 1985) will complement Tau-U findings by quantifying change over time within each phase. Level and slope changes will be examined, estimating the breakpoint for outcome improvements. This approach will model level shifts and gradual trends while considering data variability and abrupt changes (Tate & Perdices, 2018).

To address autocorrelation, lag-1 autocorrelation will be assessed, and if detected, Generalised Least Squares (GLS) regression with an AR(1) structure will be applied (Somer et al., 2022).

Reliable change in PHQ-9 will be measured via the Reliable Change Index (RCI; Jacobson & Truax, 1991), with Cronbach's  $\alpha = 0.79$  (De Man-Van Ginkel et al., 2012) and a stroke sample SD of 5.1 (Strong et al., 2021). Clinically Significant Change (CSC) will not be determined due to limited non-clinical-normative data for stroke populations. Given concerns about the comparability of PHQ-9 scores between stroke and non-stroke populations (Blake et al., 2025), data from other populations will not be considered. Instead, a cut-off of 10 will be applied to approximate clinically meaningful change, based on validated studies (De Man-Van Ginkel et al., 2012; Negeri et al., 2021; Williams et al., 2005).

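### The hypothesised order of improvement rests on breakpoint point estimates with no uncertainty or decision rule, and the break used for level and slope change is left ambiguous

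*Combined protocol and SAP*

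**What the plan says.** The opening statement of aims gives a directional hypothesis about relative timing: "It is hypothesised that wisdom will improve first, followed by gains in identity clarity or self-esteem". It then adds: "Finally, mood regulation is expected to improve last". The Design section says that "the study will pre-specify hypotheses, predetermine baseline durations", and describes replication "with each participant serving as an independent test" of the intervention's effects. Four visual analogue items carry the outcomes: "Participants will rate their agreement with four daily statements".

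The Analysis section assigns the methods as follows.

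- **Visual analysis** is described only for variability within phases (the 25% stability envelope).
- **Tau-U** compares phases: "To assess whether VAS ratings during the intervention phase are higher than baseline, Tau-U".
- **Piecewise regression** "will complement Tau-U findings by quantifying change over time within each phase". The next sentence reads: "Level and slope changes will be examined, estimating the breakpoint for outcome improvements".
- **GLS with AR(1) errors** follows if lag-1 autocorrelation is found. It is not tied to the breakpoint estimate.

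**The concern.** There are two gaps, both in the piecewise regression paragraph.

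**Order.** The hypothesis compares the timing of four outcomes within a person. Tau-U compares whole phases and cannot date a change, so the estimated breakpoint is the only tool available. The plan gives it no search range, no interval, no comparison between outcomes and no tie rule. It does not say whether one or both of identity and self-esteem must change between wisdom and mood, or how many of the three participants must show the order. Followed as written, the order would be read from four point estimates, with the rule chosen after the data are seen.

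**Break.** The description by phase, together with baseline lengths set in advance, points to a break at the known phase change. The following sentence ties level and slope changes to an estimated breakpoint. These are different analyses. A level or slope change taken at the day that fits best has been selected for being large, and cannot be judged as though the day had been fixed beforehand.

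**Working it through.** The plan states no alpha, effect size, VAS standard deviation or breakpoint precision, so there is no figure of its own to reproduce.

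**Inputs from the documents.** Three participants; baselines of 2, 3 or 4 weeks (14, 21 or 28 days); six weekly sessions; four daily items.

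**Assumptions, not in the documents.** The intervention phase lasts 42 days, so series have 56, 63 or 70 days. Residual SD is 1 cm, lag-1 correlation is 0 or 0.3, and the four items are independent within a person. Shapes and sizes of change are given with each result.

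**1. Order by chance.** Four outcomes have 4! = 24 orders.

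- Strict reading (wisdom first, mood last): identity and self-esteem may fall either way, so 2 orders; p = 2/24 = 0.083.
- Loose reading (wisdom first, mood after at least one of the other two): 3! = 6 orders start with wisdom, and 2 of those put mood second; 6 - 2 = 4, so p = 4/24 = 0.167.

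Across three independent participants:

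| Reading | At least one: 1-(1-p)^3 | At least two: 3p^2(1-p)+p^3 | All three: p^3 |
|---|---|---|---|
| Strict, p = 1/12 | 0.230 | 0.020 | 0.0006 |
| Loose, p = 1/6 | 0.421 | 0.074 | 0.005 |

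The chance of seeing the order somewhere in the study therefore runs from 0.06% to 42%, depending on a rule that the plan does not state.

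**2. Outcomes that change together.** When all outcomes were simulated with the same onset and changed gradually, the estimated break for wisdom still preceded that for mood in about 45-50% of participants. The full strict order appeared in 1% to 8% across abrupt and gradual settings. Ties, which count against the order, keep this at or below the exchangeable figure.

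**3. Recovery of a true order.** True onsets were at intervention days 7 (wisdom), 14 (identity and self-esteem) and 21 (mood). A level-and-slope model was fitted, with the least-squares break taken for each outcome.

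| Shape of change | Break searched over | Strict order recovered |
|---|---|---|
| Abrupt, 3 SD | intervention phase | 87-99% |
| Abrupt, 2.5 SD | whole series | 67-93% |
| Abrupt, 1.5 SD | whole series | 22-42% |
| Gradual to end of phase, 3 SD | intervention phase | 10-15% |
| Gradual to end of phase, 1.5 or 2.5 SD | whole series | 9-20% |

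The choice of model matters as much as the shape. A continuous change-in-slope model applied to abrupt 3 SD shifts recovered the order in only 0.3% to 8% of participants.

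**4. Which break.** Null series were tested for level plus slope change with a 2-df F test at a nominal 5%, errors independent:

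- break fixed at the phase change: 4.8-5.0% rejected;
- best-fitting day in the intervention phase: 38-42%;
- best-fitting day in the whole series: 50-55%.

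With lag-1 correlation of 0 or 0.3 and a 36- or 42-day phase, the searched versions gave 36-62%.

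**The case against.** The best defence is one of scope. The study's question is whether mood improves, and Tau-U and the PHQ-9 analysis answer that without using a breakpoint. The order is a secondary expectation about mechanism. The chance figures are modest if two of three participants are required (2.0% strict). This stands, and it limits the weight of the point. It does not remove the gap, because no such requirement is written down.

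Three stronger readings are tempting, and the documents do not support them.

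- **That the analysis would usually miss a true order.** A reader might take a low recovery rate as the headline. The low rates come from assuming slow ramps. The Analysis section expects the model to handle level shifts and abrupt changes as well as gradual trends, and recovery is high for large abrupt shifts. No single figure is justified.
- **That the plan's level and slope results carry a 40-60% false-positive rate.** The plan says these changes will be examined; it states no test and no alpha for them, and its description by phase points to the known phase change. The inflation is conditional on a reading that the text permits but does not adopt.
- **That the intervention-versus-baseline conclusion is compromised.** It is not, because Tau-U compares phases at the known phase change.

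**Conclusion.** The concern holds in limited form. A stated hypothesis about order has no analysis that could support or refute it beyond comparing point estimates by eye. That gap follows from the text and needs no simulation. Its size depends on the unstated rule: 8.3% per participant by chance (23% for at least one of three) under the strict reading and 16.7% (42%) under the loose one, assuming exchangeable breakpoints without ties and independent participants. Recovery of a true order ranges from about 10% to 99% over the assumed shapes and sizes with a level-and-slope model. That spread is itself a reason to report intervals.

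The question of the break is an ambiguity that one sentence would settle, and it has consequences only if level and slope change are tested at an estimated day. The plan should be amended on both points. Neither threatens the main mood result, so the priority is minor to moderate.

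**What to change.** 1. State that level and slope change are estimated and reported with the break fixed at each participant's phase change.
2. Label the order of improvement exploratory and descriptive by default. For each participant, report the between-outcome differences in estimated breakpoint with AR(1) bootstrap intervals. Resample whole days so that the four same-day ratings stay together. Name the model and search range in advance. The model should allow both a level and a slope change, since a continuous change-in-slope model does badly under level shifts.
3. Date only outcomes that show improvement over baseline. Least squares returns a break for every series, including flat or worsening ones.
4. If an order is to be claimed, require the interval for every pairwise difference it needs to exclude zero. State beforehand whether one or both of identity and self-esteem must change before mood, and how many of the three participants must show the order.

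The cost is analysis wording and a bootstrap; no new data and no added burden on participants. The downside is that the sequence will often be inconclusive. In a check with the continuous change-in-slope model and gradual change, 95% intervals for mood minus wisdom had median widths of 31-59 days with a baseline slope and 17-27 days with a flat baseline. Widths under the level-and-slope model were not computed. This is why exploratory labelling is the realistic default.
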